10.14 Treatment Compliance

The following parameters will be derived within each study period for treatment compliance summaries:

- Total dose administered = number of dose administered days * 60 mg
- Total dose assigned = 28 days * 60 mg

Total dose administered & assigned will only be calculated for LAT8881 group, and will be identified as '-' for Placebo group.

- Treatment compliance (%) = _____ *100

*Total number of capsules = number of dose administered days * 2 (2 capsules per day, 30 mg each)*

- Treatment Duration (days) = (Date of Last Dose – Date of First Dose) + 1

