7.10 Doses and treatment regimens

Subjects will be instructed to take one capsule with water at approximately 12 hour intervals (morning and evening) at least 30 minutes before food. Once the dosing times are established, the subject should attempt to take the capsule at the same times throughout the treatment periods. If more than 16 hours has elapsed since the last dose, the dose should be missed and the next dose taken at the regular scheduled time.

Subjects will be instructed to return to the clinic on Days 28 and 77 without taking their morning dose.

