7.12 Treatment compliance

Subjects will be asked to return their IMP bottles for a capsule count at each treatment visit.

Study drug accountability forms will be kept by pharmacy during the study and will be reviewed by the study monitor. Treatment compliance will be recorded in the subject's source documents and the CRF.

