9.2 Per protocol population

The Per Protocol (PP) population will include all subjects who received at least one dose of IMP and excludes subjects with <80% treatment compliance or who have other major protocol deviations impacting the study endpoints. Deviations for exclusion from the PP population due to inadequate exposure to IMP or completeness of primary efficacy endpoint will be determined during blinded review meeting. Per-protocol population will be defined for each study period separately.

The PP population is the primary population to analyse efficacy endpoints. Demographic and baseline characteristics of the PP population will also be presented.

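### SAP 10.14 builds total dose and the compliance term from an undefined count of dosed days, although dosing is twice daily and capsules are counted; total dose can be overstated and the 80% per-protocol rule may misclassify subjects

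*SAP*

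**What the plan says.** SAP 10.14 (Treatment Compliance) gives these derivations for each study period:

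- Dose given: "Total dose administered = number of dose administered days * 60 mg".
- Dose planned: "Total dose assigned = 28 days * 60 mg".
- Capsules: "Total number of capsules = number of dose administered days * 2 (2 capsules per day, 30 mg each".
- Compliance: "Treatment compliance (%) = _____ *100". The numerator and denominator are blank in the text I have. The percentage-change formula in SAP 10.13 is blank in the same way, so I treat this as a loss in reading the file and not as a gap in the plan.

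The total dose is calculated for the LAT8881 group only. Treatment duration is a separate quantity, running from first to last dose date. Nothing in 10.14 says what makes a day count as dosed.

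SAP 9.2 defines the per-protocol (PP) population, which "excludes subjects with <80% treatment compliance". PP is set separately for each period and is the primary population for efficacy. Exclusions for too little exposure are also left to the blinded review meeting. SAP 11.7.3.1 reports total mg and percent compliance in the exposure table.

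The protocol works in doses. Section 7.10 has one capsule roughly every 12 hours and adds: "If more than 16 hours has elapsed since the last dose, the dose should be missed". Section 7.11 counts its limit on temporary suspension in doses. Section 7.12 states: "Subjects will be asked to return their IMP bottles for a capsule count at each treatment visit". Section 7.9 puts the number of remaining capsules on the CRF.

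**The concern.** The day is the wrong unit for a twice-daily regimen. A day on which one of two capsules was taken is neither a full day nor a missed one, and the SAP has no rule for it. The legible formulas contain no term for returned capsules, so the more precise data that sites are told to collect do not enter the total dose.

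Two outputs are exposed. The first is total mg in the exposure table, where the formula is fully legible and the consequence can be worked out. The second is the 80% cut-off, which decides who is in the primary efficacy population. That consequence depends on where the capsule term sits in the compliance fraction.

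**Working it through.** **Inputs.** 30 mg per capsule, two capsules a day, 28 days per period (SAP 4.5 and 10.14); 60 capsules per bottle, one bottle per period (Protocol 7.1 and 7.5); PP cut-off 80% (SAP 9.2).

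**The plan's own figure.** Dose assigned = 28 × 60 = 1680 mg. In capsules, 28 × 2 = 56, and 56 × 30 = 1680 mg. The two agree for a fully compliant subject.

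**Where the cut-off falls.** 0.80 × 56 = 44.8 capsules. A subject who takes 45 or more passes. One who takes 44 (44/56 = 78.6%), and so misses 12, fails.

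**Total dose**, if any day with at least one capsule counts as dosed:

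| Pattern over 28 days | Capsules taken | Dose taken (× 30 mg) | Dosed days | Dose credited (× 60 mg) |
|---|---|---|---|---|
| 12 single misses on 12 days | 44 | 1320 mg | 28 | 1680 mg |
| One capsule every day | 28 | 840 mg | 28 | 1680 mg |
| 6 whole days missed | 44 | 1320 mg | 22 | 1320 mg |
| Stops after 14 full days | 28 | 840 mg | 14 | 840 mg |

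Single misses are invisible. Whole missed days and early stopping are credited correctly.

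If instead only days with both capsules counted, the error would reverse. Twelve single misses would leave 16 days, or 16 × 60 = 960 mg against 1320 mg taken. One capsule a day would give 0 mg against 840 mg. Neither definition handles a half-dosed day.

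**Compliance**, under the two natural places for the capsule term, again counting any-dose days:

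| Pattern | True (taken/56) | A: term as numerator, (2 × dosed days)/56 | B: term as denominator, taken/(2 × dosed days) |
|---|---|---|---|
| 12 single misses on 12 days | 78.6% | 56/56 = 100% | 44/56 = 78.6% |
| One capsule every day | 50% | 56/56 = 100% | 28/56 = 50% |
| 6 whole days missed | 78.6% | 44/56 = 78.6% | 44/44 = 100% |
| Stops after 14 full days | 50% | 28/56 = 50% | 28/28 = 100% |

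Under A, single misses pass the 80% rule when they should fail it. Under B, missed days and early stopping do. Each placement is right exactly where the other is wrong.

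**The case against.** **A reader might infer that both kinds of miss leave both measures unchanged, or that the half-dosed subject and the early stopper would both pass the 80% rule.** The documents do not support that. A whole missed day lowers the dosed-day count and therefore total dose. The two compliance errors need opposite positions of the same term. Both kinds of miss would vanish together only if dosed days meant the first-to-last-dose span, used as numerator over 56, with the missed days inside the span. SAP 10.14 does not say this, and it defines duration separately.

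**The link to the primary population rests on a formula that cannot be read.** This stands, and the PP consequence is therefore conditional. Under B, the half-dosed day is counted correctly for compliance, though not for total mg, which has its own legible formula.

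**The count is undefined, not shown to be wrong.** This also stands in part: the mg figures depend on counting any-dose days. The alternative of counting only fully dosed days gives an error in the other direction.

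**There are other safeguards.** Blinded review can exclude for inadequate exposure, and reviewers can see the capsule counts. SAP 11.2 has a deviation category for the investigational product. All efficacy summaries are repeated in the FAS (SAP 11.6), which does not use compliance. A subject who leaves the study at Day 14 has no week 4 mean, because SAP 10.15.1 sets a week with fewer than five ratings to missing. Misclassification needs at least 12 of 56 capsules missed, and the documents give no frequency for that. These points limit the likely effect. They do not correct the mg formula, and discretionary review is a weaker control than a correctly derived cut-off.

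**Conclusion.** The point holds in two parts.

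1. **Total dose.** On the legible formula, and if any-dose days count, mg administered is overstated for missed single doses, by up to a factor of two (1680 mg against 840 mg). Wholly missed days are handled correctly. Because mg is calculated for LAT8881 only, the overstatement concerns reported active exposure.
2. **PP rule.** Under either natural placement of the capsule term, one pattern of under-dosing below 80% scores 100%. It is single misses if the term is the numerator over 56, and missed days or early stopping if it is the denominator. The two do not occur together, and blinded review may catch some cases. The compliance formula in the source file would show which applies.

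How many subjects would be affected is unknown, and no effect on the treatment estimate is shown. The sample size is untouched. The change should still be made, because the rule governs the primary population and a better measure is already being collected.

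**What to change.** Replace the day-based terms in SAP 10.14, separately for each period:

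- Capsules taken = capsules dispensed (60) − capsules returned.
- Total dose = capsules taken × 30 mg (LAT8881 only, as now).
- Compliance = capsules taken / planned capsules × 100, with 56 planned for a nominal period. Adjust for visit windows: with Day 28 ± 1, the first period can run 27 to 29 days, so 27 × 2 = 54 to 29 × 2 = 58 capsules.

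Use these for the exposure table and the PP flag. If the sponsor wants compliance over time on treatment for subjects who stop early, state that as a separate measure.

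Two practical rules are needed. One covers unreturned bottles or missing counts. The other says which count closes each period. The Day 28 and Day 77 evening doses follow those visits, and the protocol asks for the bottles again at Day 50 (8.3.3) and at the End of Study visit (8.6.3).

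The cost is SAP wording and derivation code. The protocol already sends remaining-capsule counts to the CRF; the SAP team should confirm that a closing count is entered for each bottle.

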10.15 Efficacy Endpoints

10.15.1 NPRS Mean Scores

NPRS mean daily score ranging from 0 (no pain) to 10 (worst imaginable pain) will be derived at baseline and weeks 1 to 4 for each treatment period. Baseline mean score is defined in Section 10.12.2. The mean daily pain score each week during treatment is the arithmetic mean of the last 5 available ratings of daily pain recorded in each 7 day period within each treatment period. Standard deviations (SD) of the mean scores will be included in analyses datasets. If a subject has <5 non-missing ratings, the mean score will be set to missing for the respective week.

10.15.2 Short form BPI

Short form BPI total mean score ranging from 0 (does not interfere) to 10 (completely interferes) is the arithmetic mean of seven items. No correction will be done for missing data if the subject has omitted a few items. Mean scores will be calculated on the available items.

10.15.3 SF-MPQ-2

SF-MPQ-2 total mean score is the arithmetic mean of available scores ranging from 0 (no pain) to 10 (worst imaginable pain). No correction will be done for missing data if the subject has omitted a few items. Mean scores will be calculated on the available items.

10.15.4 NPSI

NPSI total score is the sum of the scores of the 10 descriptors ranging from 0 (no pain) to 100 (worst imaginable pain). The total score will not be calculated if data is missing in at least one of the subscales.

10.15.5 BDI-II

BDI-II total score is the sum of the scores of the 21 items ranging from 0-63. The total score will not be calculated if data is missing in at least one of the subscales. Total score of 0–13 is considered minimal range, 14–19 is mild, 20–28 is moderate, and 29–63 is severe.

10.16 Analysis Flags

10.16.1 Responder

Subjects achieving $\geq 30\%$ and $\geq 50\%$ reduction in mean NPRS score from baseline to the end of 4 weeks treatment in each study period will be separately flagged for analysis. Subjects who achieved the reduction will be flagged as '1' and who did not will be flagged as '2'.

10.16.2 Maximum Reduction

For NPRS scores, maximum reduction from baseline (that is, maximum negative change from baseline) for a subject within each study period will be flagged. Time to maximum change in days and week at which maximum reduction was attained will be included.

10.16.3 Baseline NPRS Variability

Baseline NPRS mean score will be recorded along with the respective standard deviations for each subject. Subjects will be sorted by SD (highest to lowest) for the first baseline results. Subjects having variability in quartiles 1 to 3 (i.e., 75%), will be flagged for analysis (i.e. subjects with the 25% most variable baseline results for treatment period 1 will be excluded).

11 Statistical Analyses

Summaries will be based on treatment sequence for the following:

- Subject Disposition
- Demographic and Baseline Characteristics
- Prior Medications
- Medical / Surgical History

“Total” columns will be included in these summaries. For all other analyses, summaries will be based on treatment overall and within study periods.

Following conventions will be used for the choice of treatment sequence / group in summaries:

- FAS Population – Planned treatment sequence / group
- Safety Population – Actual treatment sequence / group
- Per-protocol Population – Actual treatment sequence / group
- ██████████ Actual treatment sequence / group

Analysis of Plasma concentration and Pharmacokinetic data will be done separately, and not included in this Statistical Analysis Plan.

11.1 Subject Disposition

Following categories will be summarized in subject disposition table:

- Subjects enrolled (who met all the inclusion criteria and none of the exclusion criteria) – frequency (n)
- Subjects in FAS population – frequency (n)
- Subjects in Safety Population – frequency (n) and percentage (%) based on FAS
- Subjects in Per-Protocol Population – frequency (n) and percentage (%) based on FAS

- Subjects in [REDACTED] – frequency (n) and percentage (%) based on FAS
- Subjects completed the study, subjects who attended each visit within each study period frequency (n) and percentage (%) based on FAS
- Subjects who terminated the study along with reasons - frequency (n) and percentage (%) based on FAS
- Study duration in days – n, mean and standard deviation, median, minimum, maximum

Note that FAS population will be displayed by planned treatment sequence and all other categories will be displayed by actual treatment sequence. Reasons for discontinuation will be sorted by descending order of frequency within the “Total” column.

In DDP: Table 14.1.1.1

Subject disposition, analysis populations, status of inclusion/exclusion criteria, subjects excluded from analysis population along with reasons and unblinding details will be listed by subject. In DDP: Listing 16.2.1.1, Listing 16.2.1.2, Listing 16.2.1.3 and Listing 16.2.3.1

11.2 Protocol Deviations

Number and percentage of subjects with any deviation and number of deviation events will be summarized by treatment within each study period. The same will be sub-classified by category (major/minor) and description as follows:

- Inclusion / Exclusion
- Investigational Product
- CCMeds
- Lab
- Visit Schedule
- Procedures / Tests
- Randomisation
- Safety Reporting
- Protocol Specific Discontinuation Criteria
- Other

Deviation categories will be displayed in the descending order of frequency of total number of deviations in LAT8881 group (both study periods). Percentages will be based on Safety population. Protocol deviations occurring between screening and washout periods will be counted in Period 1, and those occurring between second baseline period until follow-up will be counted in Period 2.

In DDP: Table 14.1.2.1

Protocol deviations will be listed by subject.

In DDP: Listing 16.2.2.1

11.3 Demographic and Baseline Characteristics

Demographic and baseline characteristics will be summarized by treatment sequence. Categorical and continuous variables will be provided in the same table. The following variables will be presented: age (years), sex, ethnicity, race, childbearing potential, neuropathic pain history (PHN or DPN), PD-Q (scores and categories). The latest non-missing PD-Q results will be included in this summary.

Percentages for childbearing potential will be based only on the female population. The summary will be repeated for FAS, safety, per protocol and [REDACTED] (as per ICH E3 Guidelines). In DDP: Table 14.1.3.1 to Table 14.1.3.4

Subject demographics, neuropathic pain history and PD-Q scores and categories will be listed by subject.

In DDP: Listing 16.2.4.1, 16.2.4.3, 16.2.4.4

11.4 Medical History and Concurrent Diseases

The number and percentage of subjects with any medical history and number of mentions will be summarized by treatment sequence. The summaries will be provided by body system class. Body system class will be displayed in the descending order of frequency of number of mentions in "Total" column. Percentages will be based on the safety population. The summary will be repeated for concurrent diseases.

In DDP: Table 14.1.4.1, Table 14.1.4.2

Medical history and concurrent diseases will be listed by subject and body system. In

DDP: Listing 16.2.4.2

11.5 Prior and Concomitant Medications

The number and percentage of subjects who have taken any prior medication and number of mentions will be summarized by treatment sequence. Medications will be classified by Therapeutic Main group (ATC Level 2) and Chemical Subgroup (ATC Level 4). The therapeutic main group and chemical substance group will be displayed in the descending order of frequency of total number of mentions in LAT8881 group (both study periods). Medications will be coded using the World Health Organization's Drug-Dictionary (WHODD) version March 2019 or later. The summary will also be presented for concomitant medications by treatment overall and within each study period separately. The summary by treatment overall will only include both 'Ongoing' and 'New' medications within each treatment and counted once in 'Total' column. Percentages will be based on the safety population.

In DDP: Table 14.1.5.1, Table 14.1.5.2.1, Table 14.1.5.2.2

Prior and Concomitant medications will be listed by subject and therapeutic subgroup. Use of prohibited medications will be recorded as protocol deviations and will be listed in 16.2.2.1.

In DDP: Listing 16.2.4.5

11.5.1 Rescue Medications

Number and percentage of subjects who have taken any rescue medication will be summarized along with cumulative dose (mg) taken by treatment overall and within each study period. Extent of further analyses of rescue medications will be decided during the blinded review meeting.

Rescue medication will be listed by subject. In

DDP: Table 14.1.5.3, Listing 16.2.4.6

11.6 Efficacy Analyses

All Efficacy summaries will be based on the Per-Protocol population and repeated for the FAS population.

11.6.1 Primary Efficacy analyses – Mean daily NPRS scores

11.6.1.1 Descriptive summary

Descriptive summaries of NPRS mean scores, absolute change and % change from baseline results will be presented by treatment overall and within each study period. Visits to be included in this table are: Visit 2/5 (Baseline), Weeks within Study period: Week 1, Week 2, Week 3, Week 4. The summary will be repeated for Per-Protocol and FAS populations.

Daily NPRS scores, mean scores and standard deviation, absolute change and percentage change for each week will be listed for all enrolled subjects.

In DDP: Table 14.2.1.1 to 14.2.1.2, Listing 16.2.6.1.1, Listing 16.2.6.1.2

11.6.1.1.1 NPRS at timepoints

For per-protocol subjects with NPRS collected at timepoints in baseline and week 4 visits, descriptive summaries of NPRS mean scores, absolute change and % change from baseline results will be presented by study period and total including timepoints 0.5, 1, 2, 4 and 6 hours after the dose of IMP at Visit 2/Visit 5 and Visit 4/Visit 7.

In DDP: Table 14.2.1.3

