All subjects will take their second Day 77 IMP dose in the evening. They will be asked to discontinue their IMP after taking the Day 77 evening dose.

End of Study (Day 91)

At the end of study visit, weight, vital signs, a targeted physical examination, concomitant medications and adverse events will be recorded. Blood and urine samples will be taken for safety analysis.

Early withdrawal

Subjects who withdraw early will be asked to attend an end of study visit. This visit should be scheduled approximately two weeks after the last dose was taken.

Statistical Analysis

With a total sample size of 44 evaluable subjects there is 90% power to demonstrate a statistically significant difference in the mean change from baseline NPRS for the active treatment compared with placebo of at least 1 unit. This assumes that the standard deviation of the change from baseline NPRS is 2, the correlation between active and placebo responses within a subject is 0.5 and there is a 2-sided test at the 5% level of significance. Assuming a 20% dropout rate, it is aimed to enrol at least 55 subjects to obtain 44 evaluable subjects.

The number of subjects within each treatment group is also sufficient to show a statistically significant change from baseline of 2 or more points on the NPRS.

The primary efficacy endpoint is the change from baseline mean NPRS score to the end of treatment mean NPRS score after LAT8881, compared with the change from baseline after placebo treatment. This will be analysed in the per protocol (PP) population, which will be defined in a statistical analysis plan (SAP) before database lock. The PP will be based on the duration of IMP treatment and protocol deviations.

Mixed effects regression models will be used to compare the absolute and percentage changes from baseline to the end of each treatment for the mean NPRS scores. The models will have fixed effects for period and treatment. Baseline mean pain score within each period by treatment combination will be included as a covariate. A random effect for subject will be included to capture the repeated measures nature of the design.

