13.2 Sample size

The sample size estimation is based on the following assumptions:

- Power of 90%
- The mean change from baseline NPRS for the active treatment compared with placebo is at least
 1 unit
- Standard deviation of the change from baseline in NPRS pain score is 2
- Correlation between active and placebo response is 0.5
- The test is two sided
- The dropout rate is 20%

The number of subjects within each treatment group is also sufficient to show a statistically significant change from baseline of 2 or more points on the NPRS.

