7.2 Secondary Efficacy Endpoints

1. *Change in NPRS score at 0.5, 1, 2, 4 and 6 hours after the first dose of IMP in each treatment period, compared with the score recorded no more than 60 minutes before the first dose of IMP in that treatment period (PK subjects only)*
2. *Change in NPRS score at 0.5, 1, 2, 4 and 6 hours after a single dose of IMP, following four weeks treatment with IMP in each treatment period, compared with the score recorded no more than 60 minutes before this dose (PK subjects only)*
3. *Change in mean pain scores from baseline after 1, 2 and 3 weeks of dosing with IMP in each treatment period, using an 11 point NPRS. Pain scores at weeks 1, 2 and 3 are defined as the mean of the last five available ratings of daily pain in the subject diary, recorded in the previous 7 days of treatment*
4. *30% responder rate, based on the proportion of subjects achieving $\geq 30\%$ reduction in mean NPRS from baseline to the end of 4 weeks treatment in each treatment period*
5. *50% responder rate, based on the proportion of subjects achieving $\geq 50\%$ reduction in mean NPRS from baseline to the end of 4 weeks treatment in each treatment period*
6. *Maximum change in mean NPRS from baseline after 1, 2, 3 or 4 weeks treatment in each treatment period*
7. *Change in functioning from baseline to the end of 4 weeks treatment in each treatment period, as measured by the BPI interference scale*
8. *Change in pain characteristics and intensity from baseline to the end of 4 weeks treatment in each treatment period, as assessed by the SF-MPQ-2*
9. *Change in neuropathic pain symptoms from baseline to the end of 4 weeks treatment in each treatment period, as assessed by NPSI*

10. *Change in emotional functioning from baseline to the end of 4 weeks treatment in each treatment period, as assessed by the BDI-II*
11. *PGIC at the end of each four week treatment period*
12. *Paracetamol (rescue medication) use per week over each treatment period compared with the preceding baseline*

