7.5 Exploratory endpoints

1. *Association between change in mean NPRS from baseline to the end of four weeks treatment and selected subject baseline characteristics, including clinical diagnosis and pre-treatment [REDACTED]*
2. *Change from baseline in [REDACTED] [REDACTED] to the end of 4 weeks treatment, in each treatment period*
3. *Correlation between plasma LAT8881 concentration and the change in mean NPRS from baseline to the end of four weeks treatment in PK subjects*
4. *Change in mean NPRS score from baseline to the last week of each treatment period, after omission of subjects with the 25% most variable first baseline NPRS scores*

8 Statistical Methods

Efficacy endpoints will be summarized in a descriptive manner and analyzed using statistical methods described in section 11.7. The level of significance for statistical tests will be 0.05 and all tests will be two-sided. All p-values will be displayed to four decimal places, with p-values less than 0.0001 presented as '<0.0001' and p-values greater than 0.9999 presented as '>0.9999'. All analyses will be done using SAS [REDACTED]

Safety endpoints will be summarised in a descriptive manner.

Continuous data will be reported using the following descriptive statistics:

1. Number of observations (n)

2. Mean and standard deviation (SD)
3. Minimum (min) and maximum (max)
4. Median

Minimum and maximum values will be reported to the precision of the endpoint reported with maximum of three decimal places; the mean will be presented with one decimal place more and the standard deviation two decimal places more than the precision of the endpoint reported. Categorical data will be presented using frequency (n = number of subjects; m = number of events) and percentage (%).

Listings will be provided for all data recorded in eCRF to study subject profiles. All listings will be sorted by treatment sequence, subject ID, study period and date (if applicable). Unscheduled visit data will only be listed and not included in summaries.

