11.7.3.4 Electrocardiogram Assessments

Number and percentage of subjects with overall findings (Normal, Abnormal Not CS and Abnormal CS) will be summarized by treatment overall and within each study period and visit. Percentages will be based on safety population.

In DDP: Table 14.3.6.1

ECG findings will be listed by treatment sequence, subject ID, treatment period and visit.

In DDP: Listing 16.2.9.3

12 Changes to Planned Analyses

- Mixed Effect Regression analyses for change from baseline in NPRS mean scores is combined for weeks 1-4 within the same model, instead of week 4 and weeks 1-3 separately as defined in study protocol.
- McNemar's test is included to compare proportion of subjects achieving $\geq 30\%$ and $\geq 50\%$ reduction in mean NPRS scores across study periods.
- Analysis of covariance is included to see the effect of treatment and placebo in maximum reduction from baseline adjusting for baseline NPRS mean scores and time taken to reach maximum reduction.
- Mixed Effect Regression analyses for change from baseline in NPRS mean scores including clinical diagnosis (PHN, DPN) and baseline [REDACTED] as additional covariates is

considered as secondary analyses instead of exploratory analyses since subgroups PHN and DPN were considered clinically relevant.

- PK Analyses is not included in this Statistical Analysis Plan, and will be done separately. PK Population is replaced with Per-Protocol population for subjects with NPRS assessments taken at timepoints in baseline and Week 4 visits.

13 Index of Tables, Listings and Graphs

Refer LAT-NP-001_Data Display Plan (Ver: 2.00) for the list of Tables, Listings and Graphs.

14 References

1. ICH. ICH Harmonized Tripartite Guideline: Statistical Principles for Clinical Trials E9. 1998.
2. ICH. ICH Harmonized Tripartite Guideline: Structure and Content of Clinical Study Reports E3. 1995.

15 Appendices

15.1 painDETECT questionnaire

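### The first-dose (0.5 to 6 hour) NPRS analyses use per-protocol subjects, so a complete Day 1 or Day 50 profile can be excluded for later non-compliance in that period, and the SAP is inconsistent on whether an FAS version exists

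*SAP*

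**What the plan says.** SAP 7.2 lists as its first secondary endpoint "Change in NPRS score at 0.5, 1, 2, 4 and 6 hours after the first dose of IMP in each treatment period", measured against a pre-dose score taken within the preceding hour, in PK subjects only. SAP 3.2 makes the effect over six hours after a single dose the first secondary objective.

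The population is set in three places:

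- SAP 11.6.1.1.1 (summaries) applies "For per-protocol subjects with NPRS collected at timepoints in baseline and week 4 visits" and cites one table, 14.2.1.3.
- SAP 11.6.1.2.1 (model) uses the same per-protocol wording and cites one table, 14.2.2.3.
- SAP Section 12 declares the change from the protocol: "PK Population is replaced with Per-Protocol population for subjects with NPRS assessments taken at timepoints in baseline and Week 4 visits".

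SAP 9.2 defines a PP population that "excludes subjects with <80% treatment compliance" or who have other major deviations affecting the endpoints. It leaves exclusions for inadequate exposure or incomplete primary-endpoint data to the blinded review, and it defines PP separately for each period.

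Two general statements point the other way. SAP 11.6 says efficacy summaries are based on PP and repeated for the FAS. Protocol 13.5 says all summary tables and results will also be presented for the FAS.

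**The concern.** A first-dose response over six hours should be analysed in those who took the first dose and were rated. Compliance in the rest of the period comes after the endpoint and cannot change it. Selecting on it gives up the simple all-dosed comparison. The analysed set then depends on adherence, and possibly on tolerability, which may differ between LAT8881 and placebo.

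Protocol 13.5.1 planned these analyses simply in PK subjects. The PK population in Protocol 13.3.4 required one dose and one post-dose PK sample, with exclusions only for clinically significant events or deviations that compromised the PK results. It had no adherence threshold. Section 12 of the SAP declares the switch to PP but gives no reason why PP suits a single-dose question. With 15 subjects, each unnecessary exclusion counts.

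**Working it through.** **1. The plan's own figure.** The documents give no sample size or power for the timepoint analyses. The only stated figure is for the primary endpoint: "With a total sample size of 44 evaluable subjects there is 90% power" to detect 1 NPRS unit (Protocol synopsis). Inputs are SD 2, correlation 0.5 and a 20% dropout rate (Protocol 13.2), with two-sided 5% tests (SAP Section 8).

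- SD of the within-subject difference = 2 × √(2 × (1 − 0.5)) = 2.0.
- Normal approximation: n = ((1.960 + 1.282) × 2 / 1)² = 42.03, so 43.
- Noncentral t with n = 44: power 0.900 on 43 df.
- Enrolment: 44 / 0.8 = 55.

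The plan's figure reproduces, and nothing in this point changes it.

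**2. When the endpoint is complete, and when PP is decided.**

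| Item | Timing | Source |
|---|---|---|
| First dose of each period, supervised | Day 1, Day 50 | Protocol 2.1 and 2.2, footnotes |
| PK subjects remain in clinic and are rated | to 6 hours | Protocol 8.3.1, 8.6.1 |
| Compliance below 80% | over the period | SAP 9.2, 10.14 |
| Exposure and completeness exclusions | blinded review | SAP 9.2 |

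The last two rows come after the endpoint is complete.

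**3. What the compliance rule can do.** The fraction in SAP 10.14 is not legible in the text available. As an assumption, count capsules taken against 28 × 2 = 56 planned per period. The threshold is 0.80 × 56 = 44.8 capsules.

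- Missing 11: 45/56 = 80.4%, stays in PP.
- Missing 12: 44/56 = 78.6%, leaves PP for that period and takes a complete first-dose profile with it.

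The 0.5 to 6 hour scores of these two subjects are equally valid.

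**4. Reach across periods.** Because PP is period-specific, Period 2 non-compliance does not remove Day 1 data, and Period 1 non-compliance does not by itself remove Day 50 data. It can still remove one half of a subject's first-dose pair.

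**5. Is there an FAS version?** The weekly NPRS sections name both populations locally and cite two tables each (14.2.1.1 to 14.2.1.2 for summaries, 14.2.2.1 to 14.2.2.2 for the model). The timepoint sections name PP only and cite one table each. This conflicts with SAP 11.6 and Protocol 13.5.

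**6. Size.** The documents give neither a PP exclusion rate nor an SD for the 0.5 to 6 hour change, so no loss can be derived. As a range only, assumed exclusion rates of 5%, 10%, 20% and 30% of 15 subjects give expected losses of 0.75, 1.5, 3.0 and 4.5. Borrowing the primary endpoint's SD of difference (2.0) and using n − 2 df, the 95% half-width for a paired treatment difference, t × 2/√n, is 1.12 with 15 pairs, 1.29 with 12 and 1.46 with 10. These values show what pairs are worth. They do not show what the PP rule would cost.

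**The case against.** The strongest reply is that SAP 11.6 is the parent of both timepoint sections and promises the FAS repeat, as does Protocol 13.5. The FAS is all randomised subjects, so that repeat would keep every observed Day 1 and Day 50 profile. The tables themselves are defined in a Data Display Plan that is not among the documents. The protocol also makes PP primary for efficacy, and Section 12 declares the change openly. This stands to the extent that a reader cannot conclude the data are discarded outright. It does not settle the matter: a programmer working from the specific sections would produce PP only, and even with an FAS repeat the lead analysis of a six-hour endpoint would still be selected on later adherence.

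Three stronger readings are tempting but not supported.

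- **Every early withdrawal is removed.** Exposure and completeness exclusions are left to the blinded review. The legible part of SAP 10.14 counts capsules from days on which doses were given, so a subject who stops in week 1 does not demonstrably score below 80%.
- **Ratings at both visits are required.** The phrase about baseline and week 4 visits recurs in SAP 10.12.2, 10.13 and Section 12 as a label for the PK subjects. A both-visits rule is one possible reading and is nowhere stated.
- **The standard error grows by 12%.** Applying the 20% dropout rate to 15 subjects leaves 12, and √(15/12) = 1.118. But dropout is not PP exclusion, and a subject lost before Day 50 has no first-dose pair under any population. If half of three losses came before Day 50, the ratio would be √(13.5/12) = 1.06; if all did, it would be 1. The timepoint model in 11.6.1.2.1 also has no treatment term, a separate matter, so it does not estimate the contrast to which such a figure would apply.

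**Conclusion.** The point holds as a mismatch between endpoint and population, combined with an internal inconsistency. The conclusion that a first-dose profile can be excluded for later behaviour in the same period rests on SAP 9.2, 11.6.1.1.1, 11.6.1.2.1 and Section 12. Only the 12-capsule illustration depends on the assumed 56-capsule denominator. Whether an FAS analysis of these data is planned, and whether both visits are needed, cannot be settled from the text. The numerical loss is unknown. The consequence is confined to one secondary objective in 15 subjects for whom no power is claimed. The change is worth making because it costs almost nothing and removes selection on events that follow the endpoint.

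**What to change.** - For the Day 1 and Day 50 timepoints, analyse all PK subjects who took the supervised dose and have a pre-dose and at least one post-dose NPRS rating, by treatment received.
- State that ratings at both the first-dose and week 4 visits are not required for inclusion.
- Keep any PP restriction to the Day 28 and Day 77 timepoints, and provide there the FAS repeat that SAP 11.6 promises.
- Align SAP 11.6.1.1.1, 11.6.1.2.1, Section 12 and the table list in the Data Display Plan, adding the missing table numbers.

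The cost is one population flag, revised SAP wording and the matching table entries, settled before the blinded review. No new data are needed.
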